5.3.1 VMS events

Exploratory endpoints that include mild post-baseline VMS events (frequency, severity, percent reduction, and responder analyses) also consider mild VMS at baseline.

The severity of moderate to severe VMS in this Section will be calculated as described in Section 5.1 where both baseline and post-baseline severity include only moderate and severe VMS events in the calculation.

For the daily frequency of moderate and severe VMS endpoint, the baseline frequency and post-baseline daily frequency will be calculated as described in Section 5.1 In addition, the co-primary endpoints will also be re-derived excluding data affected by COVID-19.

5.3.2 Hormones

Hormones being collected include estradiol (E2), follicle stimulating hormone (FSH), luteinizing hormone (LH), sex hormone-binding globulin (SHBG), total and free testosterone, androstenedione, dehydroepiandrosterone (DHEA), and estrone.

5.3.3 Bone Markers

Bone markers being collected include Bone Specific Alkaline Phosphatase (BSAP), carboxyterminal telopeptide of Type I Collagen (CTX), Procollagen 1 N-Terminal Propeptide (P1NP). However, they only collected at the randomization and Week 52/end of treatment visit, so analyses will be described in the active treatment extension period SAP.

5.3.4 Patient Global Impression Scales (PGI-C VMS, PGI-S SD, PGI-C SD)

The PGI is comprised of 2 companion 1-item PRO measures analogous to the Clinical Global Impression (CGI) scales [Busner J & Targum SD, 2007]. These measures provide brief, stand-alone global assessments prior to and after initiating a study medication. The Patient Global Impression evaluates the following: (1) patient-perceived severity of a condition (PGI-S) and (2) patient-perceived change from the initiation of treatment (PGI-C). In this study, PGI scales will be used to evaluate meaningful within-person changes over time in VMS (PGI-C) and sleep disturbance (PGI-S and PGI-C).

The PGI-C VMS asks: "Compared to the beginning of this study, how would you rate your HFs/night sweats now?" Subject ratings range from (1) much better to (7) much worse.

The PGI-C SD asks: Compared to the beginning of this study, how well are you sleeping now?" Subject ratings range from (1) much better to (7) much worse.

The PGI-S SD asks: "How would you rate the severity of any problems you currently have while sleeping at night?" Subject ratings range from (1) no problems to (4) severe problems.

5.3.5 Patient-Reported Outcomes Measurement Information System Sleep Disturbance – Short Form 8b (PROMIS SD SF 8b)

See Section 5.2.1.1 PROMIS SD SG 8b total score will be analyzed at each visit. Based on the correspondence from the FDA in the Type B meeting minutes from April 2019, it also will be analyzed at each visit after removing question #4 - I had difficulty falling asleep.

5.3.6 Patient-Reported Outcomes Measurement Information System Sleep Disturbance – Short Form 8a (PROMIS SRI SF 8a)

The PROMIS SRI SF 8a [PROMIS Sleep-Related Impairment, 2015] is an 8-item PRO measure that evaluates self-reported perceptions of alertness, sleepiness and tiredness during usual waking hours and the perceived functional impairments during wakefulness associated with sleep problems or impaired alertness. Though this measure does not directly assess cognitive, affective or performance impairment, it does measure waking alertness, sleepiness and function within the context of overall sleep-wake function. The PROMIS SRI SF 8a is a universal rather than disease-specific instrument, and has a 7-day recall period.

Responses to each of the 8 items on the PROMIS SRI SF 8a range from 1 to 5, and the range of possible summed raw scores is 8 to 40. Higher scores indicate more of the concept measured (sleep-related impairment).

5.3.7 Menopause-Specific Quality of Life (MENQOL)

The MENQOL is a 29-item PRO measure that assesses the impact of 4 domains of menopausal symptoms, as experienced over the last week: vasomotor (items 1 to 3), psychosocial (items 4 to 10), physical (items 11 to 26) and sexual (items 27 to 29). Items pertaining to a specific symptom are rated as present or not present, and if present, how bothersome on a zero (not bothersome) to 6 (extremely bothersome) scale [Lewis et al, 2005].

Each item score ranges from 1 to 8, and each domain is scored separately; each domain mean ranges from 1 to 8 [Lewis et al, 2005; Hilditch et al, 1996]. The overall questionnaire score is the mean of the domain means. Higher scores represent more bothersome menopausal symptoms.

5.3.8 Euro-QoL 5D-5L (EQ-5D-5L) with Visual Analog Scale (VAS)

The EQ-5D-5L is a 5-item standardized measure of health status that provides a simple, generic measure of health for clinical and economic appraisal [EuroQol Research Foundation, 2018; van Reenen & Janssen, 2015]. This PRO measure comprises 5 dimensions: mobility, self-care, usual activities, pain/discomfort and anxiety/depression. Each dimension has 5 levels: no problems, slight problems, moderate problems, severe problems and extreme problems. The subject is asked to indicate her health state by selecting the most appropriate statement in each of the 5 dimensions. This decision results in a 1-digit number that expresses the level selected for that dimension. The digits for the 5 dimensions

can be combined into a 5-digit number that describes the patient's health state. The data from each of the 5 dimensions will be summarized.

The EQ-5D-5L VAS is a subject-reported measure that records the respondent's self-rated health on a vertical VAS where the endpoint is labeled 'Best imaginable health state' and 'Worst imaginable health state.' The scale ranges from 0 to 100, where 100 indicates the subject is in her best possible health state and 0 indicates the subject is in her worst possible health state. Subjects mark an 'X' on the scale to rate their health status that day.

5.3.9 Work Productivity and Activity Impairment questionnaire specific to VMS (WPAI-VMS)

The WPAI-VMS is a 6-item PRO measure that examines VMS-related work productivity and activity in the preceding 7 days [Reilly Associates, 2013; Reily et al, 1993]. It consists of 4 domains: absenteeism (the percentage of work time missed because of VMS in the past 7 days), presenteeism (the percentage of impairment experienced while at work in the past 7 days because of VMS), overall work productivity loss (overall work impairment measured by combining absenteeism and presenteeism to determine the total percentage of missed time) and activity impairment (the percentage of impairment in daily activities because of VMS in the past 7 days). If the subject is unemployed, only 2 of the 6 items on this questionnaire require completion.

WPAI-VMS outcomes are expressed as impairment percentages, with higher numbers indicating greater impairment and less productivity (i.e., worse outcomes) [Reilly Associates, 2013].

5.4 Safety Endpoints

Safety evaluations will include the following endpoints and other safety-related assessments:

- Frequency and severity of AEs
- TVUs and endometrial biopsy findings [Analysis to be described in the 52-Week SAP]
- Change from baseline to each timepoint in vital signs: sitting systolic and diastolic blood pressure and pulse rate
- Change from baseline to each timepoint in ECG parameters
- Change from baseline to each timepoint in laboratory tests: hematology, biochemistry and urinalysis

6 STATISTICAL METHODOLOGY

6.1 General Considerations

Continuous data will be summarized descriptively including the number of subjects (n), mean, standard deviation (SD), median, minimum and maximum. Categorical data will be summarized by frequencies and percentages. Percentages by categories will be based on the number of subjects with no missing data, i.e. the percentages for the non-missing categories will add up to 100%.

All statistical comparisons will be conducted using 2-sided tests controlling the overall error rate at the 5% significance level, as described in Section 6.4

All data summarization and analyses will be performed using SAS® on Unix. Specifications for table, figures, and data listing formats can be found in the Tables Listings and Figures (TLF) specifications.

As mentioned in the introduction, this analysis plan describes the analyses of the 12-week double-blind treatment period.

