6.4 Analysis of Efficacy

All statistical comparisons will be conducted using 2-sided tests at the $\alpha = 0.05$ significance level unless specifically stated otherwise. There are additional testing details below regarding the 4 co-primary endpoints. All null hypotheses will be of no treatment difference, all alternative hypotheses will be 2-sided and control for 2 comparisons to placebo using the Hochberg approach, unless specifically stated otherwise.

The family-wise type I error rate for the 2 active dose groups compared to placebo for the 4 co-primary efficacy endpoints will be controlled using a Hochberg approach. All 4 co-primary endpoints must be statistically significant for a given dose to be considered successful. Given that, the largest p-value in each dose group will be used to test that dose because it represents the least significant of the co-primary endpoints.

If the larger of the two maximum p-values, one from each dose, is less than 0.05, then both dose groups are considered statistically significant. If not, then if the smaller of the p-values is less than 0.025, the second compared dose is considered statistically significant. Othewise, neither dose is considered statistically significant. The trial will be considered successful if at least one dose is statistically significant.

All analysis of efficacy will be presented by treatment group for FAS, unless specified otherwise.

In general, the mechanism of missing data due to COVID-19 will be assumed to be missing at random (MAR).

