6.4.2 Analysis of Key Secondary Efficacy Endpoint

The PROMIS SD SF 8b scale will be analyzed using MMRM, similar to the primary analysis of the co-primary endpoints, with spatial power as the backup covariance structure.

If all the co-primary endpoints are statistically significant between fezolinetant and placebo at both doses, then the 5% alpha from the analysis of the co-primary endpoints will be passed to the key secondary endpoint as part of the family-wise error rate.

As a sensitivity analysis, the analysis will be repeated by excluding data that are impacted by COVID-19, which includes the data recorded after the subjects were diagnosed of COVID-19, after study drug discontinuation due to COVID-19, during dose interruption due to COVID-19, and visits that are out of protocol window due to COVID-19 recorded in the eCRF.

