6.4.3 Analysis of Secondary Efficacy Endpoints

The mean change in the frequency and severity of moderate and severe VMS from baseline to each week up to week 12 comes from the same model as the co-primary analyses, but examines the results at all weeks.

For percent reduction at weeks 4 and 12, an MMRM model as described in Section 6.4.1.1 will be used.

For each of the secondary responder endpoints, logistic regression will be used for the analysis for each week and endpoint. The analyses will include the treatment group and smoking status (current vs. former/never) as factors and baseline measurement (mean frequency of vasomotor symptoms) as a covariate.

For these responder endpoints, the number of subjects who achieve the reduction will be summarized by study week with descriptive statistics for each treatment arm. A Kaplan-Meier estimate will be used to estimate the time to response. Smooth average (SA) will be used for the time to response. SA value for day X-1, day X and Day X+1 would be assigned to day X. The time to response will be the first day with at least 50% (or 100%, or the exploratory endpoints 75%, 90%) response for both original numbers and SA number. For the non-responders, it will be censored at the end of the last day of the double-blind treatment (e.g., 8am the following day).

Comparisons between the fezolinetant and placebo will be calculated based on the odds ratio using a 2-tailed 95% confidence interval (CI) and p-values.

PGI-C VMS score will be analyzed using Cochran Mantel Haenszel (CMH) test with modified ridit scores.

For the changes in the frequency and severity of moderate and severe VMS from baseline to each week up to week 12 that are derived from diary data, the analysis will be repeated by excluding diary data that are impacted by COVID-19, which includes the diary data recorded after the subjects were diagnosed of COVID-19, after study drug discontinuation due to COVID-19, and during dose interruption due to COVID-19.

For the PGI-C VMS scores that are collected by visit, the analysis will be repeated by excluding data that are impacted by COVID-19, which includes the data recorded after the subjects were diagnosed of COVID-19, after study drug discontinuation due to COVID-19, during dose interruption due to COVID-19, and visits that are out of protocol window due to COVID-19 recorded in the eCRF.

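### The 12-week SAP's statement that all comparisons control the overall error rate at 5% is broader than the procedure it points to, which covers only the co-primary and key secondary endpoints

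*SAP*

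**What the plan says.** Section 6.1 of the 12-week SAP reads: "All statistical comparisons will be conducted using 2-sided tests controlling the overall error rate at the 5% significance level". The sentence ends by pointing to Section 6.4 for the description.

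Section 6.4 sets a two-sided 0.05 level as the general rule. For all null hypotheses it asks for tests that are "2-sided and control for 2 comparisons to placebo using the Hochberg approach, unless specifically stated otherwise". It then defines family-wise control for the two doses "for the 4 co-primary efficacy endpoints will be controlled using a Hochberg approach", using the largest of the four p-values for each dose.

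Section 6.4.2 adds one step. If every co-primary endpoint is significant at both doses, "then the 5% alpha from the analysis of the co-primary endpoints will be passed to the key secondary endpoint". Section 5.2.1 says the same and treats overall and family-wise as equivalent terms. No section passes alpha any further.

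Section 6.4.3 covers the remaining secondary endpoints:

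- Weekly frequency and severity, an analysis that "comes from the same model as the co-primary analyses, but examines the results at all weeks".
- Percent reduction at Weeks 4 and 12.
- Two responder definitions, each tested at every week, with odds ratios, intervals and p-values.
- A Cochran-Mantel-Haenszel test of PGI-C VMS.

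Section 6.4.4 adds the exploratory tests. The only p-value described as nominal is that of the anchor-based responder analysis in 6.4.4. Subgroup p-values are withheld under 6.4.1.3.

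**The concern.** The subject of the 6.1 sentence is every statistical comparison, and the property it promises is overall control at 5%. The default in 6.4 adjusts for two doses within one endpoint at one week. That is a narrower property, and it says nothing about the many endpoint-by-week results that will sit side by side in the tables.

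Weekly effect on frequency and severity is a stated secondary objective, so statements about time of onset, responder rates and PGI-C are foreseeable. With 6.1 as it stands, a small p-value at an early week could be cited as falling under the 5% guarantee, even if the co-primary endpoints failed, because no condition links the two. The p-values themselves would be correctly computed. What is at stake is the strength of claim a reader attaches to them.

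**Working it through.** **Step 1. Does 5% hold where the SAP defines control?** Within a dose, success needs all four co-primary p-values to be significant, so testing the largest does not inflate the error. Across two doses the allowance is 0.025 + 0.025 = 0.05. Simulating Hochberg for one pair of doses sharing a placebo arm, with no effect, gives 4.8%. The key secondary is tested only after both doses have won on all four co-primaries:

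- If either dose's co-primary null is true, reaching the key secondary already required a counted error.
- If neither is true, the key secondary is tested by Hochberg at 5%.

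So the combined error is at most 5%, and the stated figure is reproduced for this set.

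**Step 2. How many tests lie outside that set?** Call one endpoint at one week, with its two dose comparisons, a family. The SAP does not state this count; it is derived from 6.4.3 and the analysis windows in 6.10.1.1.

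| Endpoint | Weeks counted | Families |
|---|---|---|
| Change in frequency | 1 to 12, except co-primary Weeks 4 and 12 | 10 |
| Change in severity | same | 10 |
| Percent reduction | 4 and 12 | 2 |
| Responder, at least 50% | 1 to 12 | 12 |
| Responder, 100% | 1 to 12 | 12 |
| PGI-C VMS | 4 and 12 | 2 |
| Total | | 48 |

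This is 48 × 2 = 96 dose-versus-placebo tests. The endpoint list in 5.2.2 names percent reduction at every week. On that reading the total is 48 + 10 = 58. Exploratory tests are not counted.

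**Step 3. What is the error across those families if there is no effect anywhere?**

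- Independent, 5% each: 1 − 0.95^48 = 91.5%.
- Independent, at the simulated 4.8% each: 90.5%.
- Independent, 58 families at 5% each: 1 − 0.95^58 = 94.9%.
- Expected number of falsely significant families: at most 48 × 0.05 = 2.4. Correlation does not change this bound.

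Independence is not realistic, so the 48 families were simulated with Hochberg over two doses inside each and a shared placebo arm. All correlations are assumed.

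| Assumed correlation | At least one false positive |
|---|---|
| Equal, 0 | 90% |
| Equal, 0.5 | about 61% |
| Equal, 0.7 | 41% |
| Equal, 0.8 | 30% |
| Equal, 0.9 | about 20% |
| Between endpoints 0.3, between weeks 0.6 | 73% |
| Between endpoints 0.5, between weeks 0.8 | 52% |
| Between endpoints 0.7, between weeks 0.9 | 34% |
| Between endpoints 0.9, between weeks 0.95 | 20% |

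Every row is well above 5%. For comparison, a plain Bonferroni split that did cover the 48 families would need 0.05 / 48 = 0.00104 for each.

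**The case against.** The strongest reply is that 6.1 does not stand alone. It points to Section 6.4, which says plainly which tests are in the family, and 5.2.1 uses overall as another word for family-wise. Trial success is defined on the co-primary endpoints only. The protocol (7.4) has no such sentence: it gives the 0.05 level, and 7.4.1.1 and 7.4.2.1 confine family-wise control to the co-primary and key secondary endpoints. A careful reader of all these sections would reach the right scope.

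Much of that stands. It shows that the fault is in one sentence and its missing labels. It does not make the sentence accurate: following the cross-reference leads to a default for all null hypotheses that controls across doses only, while the sentence still says all comparisons.

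Three stronger readings are tempting, and the documents support none of them.

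- *That the testing strategy is wrong or the trial's type I error is uncontrolled.* The confirmatory set is controlled, as Step 1 shows. Leaving further endpoints outside it is not an error.
- *That 90% is the likely error rate.* Weekly frequency and severity come from the co-primary models, and responder status is derived from the same weekly frequency, so the tests are correlated. The documents do not say how strongly. The global null is also only one configuration, although a family-wise claim has to hold under every pattern of true and false nulls.
- *That the sponsor plans confirmatory claims from weekly or responder results.* Neither document says so.

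**Conclusion.** The point holds as an over-broad statement. The 12-week SAP controls the overall two-sided 5% error for the four co-primary endpoints at both doses and for the key secondary that follows them. The remaining secondary and exploratory p-values are outside that control, yet 6.1 includes them and nearly all lack a nominal label.

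For the secondary families alone, the illustrative error is about 20% to 90%, against the stated 5%. That range rests on the count of 48, on the global null, and on assumed equal correlations from 0.9 to 0. The direction does not depend on which correlation is chosen, but the exact size does. No power figure, sample size, computed p-value, co-primary conclusion or key secondary conclusion changes.

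**What to change.** 1. In 6.1, replace the sentence with: *The overall two-sided 5% family-wise error rate is controlled for the four co-primary endpoints at both doses and for the key secondary endpoint tested after them, and for no others; all other p-values are nominal.*
2. In 6.4, limit the default Hochberg sentence to those tests, or add that Hochberg elsewhere adjusts for the two doses only and does not make a result confirmatory. Without this, a reader would not know how a nominal p-value is to be judged.
3. Footnote the secondary and exploratory p-values as nominal in the outputs.

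The cost is two edited sentences and table footnotes, with no change to any analysis. The downside is that weekly onset, responder and PGI-C results are described less strongly. If the sponsor wants one of them to carry a controlled claim, the alternative is a testing hierarchy that places it after the key secondary, fixed before unblinding.

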6.2 Study Population

In general, data such as patient disposition, demographics and baseline characteristics will be summarized for FAS population as the definition of FAS is identical to SAF if no patients were given wrong study drug. In the event when FAS is not identical to SAF then data will be summarized for both FAS and SAF as specified in the relevant sections.

6.2.1 Disposition of Subjects

Disposition of subjects will be summarized for the FAS by treatment group and overall. Number of subjects who complete or prematurely discontinue from the 12-week treatment period will be summarized by treatment group and overall. For the discontinuations, the primary reason reported by the investigator will be summarized.

Number and percentage of subjects for each analysis set will be summarized by treatment group and overall. In addition, number and percentage of subjects excluded from the PPS4 and PPS12 by reason for exclusion will be summarized for FAS.

6.2.2 **Protocol Deviations**

The number and percentage of subjects with the following protocol deviation criteria will be summarized for SAF for each criterion and overall, by treatment group and total as well as by investigative site. Subjects deviating from a criterion more than once will be counted once for the corresponding criterion.

The unique identifiers will be as follows:

- PD1 Entered into the study even though they did not satisfy entry criteria,
- PD2 Developed withdrawal criteria during the study and was not withdrawn,
- PD3 Received wrong treatment or incorrect dose,
- PD4 Received excluded concomitant treatment.

The number of subjects who were impacted by COVID-19 will be summarized by impact item and treatment group and overall for SAF population. The impact items include treatment discontinuation, dosing change/interruption, death from COVID-19, healthcare encounter due to COVID-19, protocol deviation including missed visit windows due to COVID-19, and impacted diary data due to COVID-19.

An overview listing of subjects who were affected by COVID-19 will be generated by the impact items.

Detailed information on how these assessments are impacted by COVID-19 can be found in relevant data listings with a flag for COVID-19.

6.2.3 Demographic and Other Baseline Characteristics

Demographics, tobacco history (smoking status), substance use (e-cigarette, alcohol, cannabis), caffeine beverage intake, height and weight, and targeted medical history will be summarized descriptively by treatment group and total group for SAF. Note that current versus former or never smoking status is a stratification factor for randomization. Age group categories include ages within <40 years, >=40 years to <46 years, >=46 years to <51 years, >=51 years to <56 years, >=56 years to <61 years, >=61 years to <66 years, and >=66 years.

Medical history is coded in MedDRA, and will be summarized by System Organ Class (SOC) and Preferred Term (PT) by treatment group and total group for the SAF.

